17. DATA ANALYSIS & STATISTICAL CONSIDERATION

17.1 Analysis Overview

This is a single center, randomized clinical trial, designed to test the effect of Behavioral Weight Loss and metformin versus self-directed weight loss on blood levels of Insulin-like Growth Factor 1 (IGF1) and IGF1 to Insulin-like Growth Factor Binding Protein III (IGFBP-III) ratio over 12 months among men and women who survived malignant solid tumor after completing all local therapy and/or adjuvant chemotherapy. Participants will be randomized at a 1:1:1 ratio to self-directed weight loss (Group A), Coach-Directed Behavioral Weight Loss (Group B), or metformin pharmaceutical intervention (Group C). Randomization will be stratified by race and BMI, and we are aiming to recruit ~50% African American in this trial. 120 individuals will be enrolled, with 40 participants in each arm.

The distribution of baseline characteristics of the participants by intervention arms will be described using mean and standard deviation for the continuous variables, and % frequency for the categorical variables. The primary analyses will follow the intention-to-treat principles, and be carried out using likelihood based mixed effects linear regression modeling. Evaluation of potential impacts due to missing data, should it occur, on intervention effect estimates will be anchored on analyses assuming missing at random, and supplemented by sensitivity analyses under plausible informative missing scenarios using multiple imputation approach. Potential impacts of treatment adherence on estimates of intervention effects will be explored by on treatment analyses paying special attention to adjusting for characteristics associated with treatment adherence. These analyses will be carried out using the propensity score approaches.

17.2 General Statistical Approach

The primary endpoint of this trial is the 6-month change in level of IGF-1 and IGF1 to IGFBP-III ratio among the Coach-Directed Behavioral Weight Loss arm versus self-direct arm (B vs. A), and metformin arm compared to self-direct arm (C vs. A). Intervention effects will be analyzed using intent-to-treat. Each active intervention arm will be compared with the control arm using

likelihood based mixed effects linear regression models utilizing data from all 3 time points, i.e. baseline, 6, and 12 months, simultaneously, as following.

The primary analysis model: The mean model for the mixed effects regression will be structured to include 2 binary intervention arm indicators (for Group B and C), 3 binary followup time indicators (for 3-, 6- and 12-month follow-up), and the cross-product interaction terms between the group and time indicators (6 interaction terms), and the covariance model will employ a 4x4 unstructured covariance matrix to allow different outcome variances and account for the intra-individual outcome correlations over time. Race and baseline BMI levels, the variables used for stratifying the randomization, will be included in the mean model. Other variables found not to be balanced between the trial arms will also be included as necessary. Outcomes may be transformed as needed to satisfy the distributional assumptions for the likelihood approach.

The primary testing contrasts of this trial will be the 2 aforementioned pairwise comparisons at 6 months, which will be evaluated through the regression coefficients of the Group B by 6month interaction term (B vs. A), and Group C by 6-month interaction term (C vs. A), respectively. The secondary testing contrasts include B vs. C of change in outcomes at 6month, and the 3 pairwise group comparisons of outcome changes at 12 months, which will be evaluated using the same model through the corresponding group by time interaction terms.

For outcomes such as IGF-1, IGF-1:IGFBP3 ratio, weight, BMI, and measures assessed through the metabolic panel labs, where data will be available at 3-month, these information will be utilized through the primary model to enhance model estimation, especially in the event of missing data encountered at 6- and/or 12-month, events though the effect size of the intervention at 3-month is not part of the primary or secondary goals. For outcomes such as EQ-5D, questionnaire outcomes on dietary intake and physical activity, HbA1c, IL-6, IL-8, and CRP, where data will not be available at the 3-month visit, the analysis models will not include any independent variables terms related to that visit.

We will also conduct subgroup analyses to explore for potential differential intervention effects across these pre-specified subgroups. Statistical significance of these subgroup analyses will be evaluated though incorporating appropriate subgroup by intervention by visit interaction terms. To explore the association of physical activity levels with the outcomes of IGF-1 or the IGF-1: IGFBP-3 ratio, time dependent physical activity measures will be further included to augment the primary analysis model to explore for the degree of attenuation of intervention effect by physical activities. Similar analyses could be done for body weight and BMI.

We will also explore for possible treatment effect modification by baseline BMI level to better understand the potential heterogeneity of treatment effects to inform future trials and studies. This will be carried out by including the 3-way interaction terms (Group indicator by Time indicator by BMI) in the primary analysis model. We will also estimate total intervention costs for future trials in a large population.

Missing and incomplete data

Prevention is far superior to a statistical cure, and every effort will be made to collect outcome data on all randomized participants. For example, we will collect outcomes on individuals who have stopped participating in the trial intervention. Due to the high longitudinal correlation, missed “interior” visits won’t decrease information very much for a linear trend. However, they are needed to assess departures from a linear trend.

As detailed in Little and Rubin 2002 and discussed by Mealli , the underlying missing data process determines the biasing effects of missing data and structures valid analytic strategies.^{93,94} If data are missing completely at random (MCAR), then there is no induced bias and a complete case analysis, while inefficient, is valid. If the probability of a potential observation being missing depends on what has been observed, but not on what hasn’t been observed, i.e., data is missing at random (MAR), then estimates based on an appropriate analytic model (on both the mean and error structure) for the observed data will not be biased. Use of a valid statistical model for the observed data would allow the missing data process to be ignored. In this situation either multiple imputation (MI) or development of a valid statistical model for the observed data (appropriate mean structure and correlation structure) will allow valid statistical inferences on the intervention effects. To use all participants when comparing treatments on the (12 month - baseline) outcome changes between groups, we will take advantage of the statistical association between outcomes at baseline, 6 and 12 months, and build a longitudinal model and then use one of these essentially equivalent approaches

In the third type of missing data process the probability of being missing depends on what would have been observed (e.g., the IGF-1 that would have been measured). In this case, neither MI nor developing a model for the observed data will completely eliminate bias. One can never empirically rule out this situation, but comprehensive statistical modeling coupled with sensitivity analysis can assess the stability of findings. We will anchor our sensitivity analyses under the assumption of MAR, and derive a valid model for the observed data under MAR, then alter the mean structure of the model under plausible non-MAR scenarios, and estimate intervention effects through MI approach to examine the robustness of the finding under MAR assumption.

On-treatment Analyses

Primary analyses will be performed on an intention-to-treat basis. However, interpretation of the trial outcomes is complicated because of drop-out from the intervention group and drop-in from the control group. Particularly common are early drop-outs, i.e. individuals randomized to intervention who attend only a few intervention sessions, sometimes none. Such persons are included in ITT analyses. In this setting, we will compute “on treatment” comparisons and variations on this approach that adjust such an analysis for differential correlates of adherence in the treatment groups.

Care is needed in answering such questions, and Bellamy et al. and Mealli et al. provide a useful framework for such analyses.^{94,95} For a basic case, we consider how to handle participants who complete at most 2 intervention “courses”. They will be included in the primary, as randomized, intent to treat analysis. A secondary question is, “how do the

treatment groups compare for those who adhered to treatment?” A straightforward comparison of treatments based only on “compliers” is attractive, but is biased if the compliers differ among the treatment groups. A valid comparison depends on adjusting for these differences, being careful not to adjust away the treatment effect. Propensity score approaches using information available at randomization and up through the first “course” could adjust for this imbalance. More sophisticated approaches using time-varying propensities allow accommodating more complicated patterns of non-adherence.

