7. RANDOMIZATION AND ASSIGNMENT

Participants will be randomized to one for the three following arms:

- Self-Directed weight loss
- Coach-Directed Behavioral weight
- Metformin treatment

Randomization will be stratified by race and BMI. To prevent prediction of randomization, we will generate the randomization schedule in variable blocks sizes. A biostatistician will generate the allocation sequence. Randomization will take place after the study coordinator confirms that all screening activities have occurred, individual meets all eligibility criteria, and all baseline data have been collected. Individuals who do not meet eligibility or who lack proper documentation of eligibility or key data elements will not be randomized. An unmasked study coordinator or staff member who is not involved in follow-up data collection will carry out assignment allocation.

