16. SAMPLE SIZE

The trial has sufficient resources to enroll ~120 participants, who will be randomly allocated in equal proportions to each of 3 arms:

- Group A: Self-directed weight loss arm.
- Group B: Coach-Directed Behavioral weight loss intervention arm.
- Group C: Pharmacological intervention using metformin.

The primary contrasts are (C vs. A) and (B vs. A). The (C vs. B) contrast is secondary and is not considered in computing power.

The required sample size for the study was powered for testing 2 primary contrasts of change in IGF-1 over time in (1) lifestyle (arm B) vs. self-directed comparison (arm A), and (2) metformin (arm C) vs. self-directed comparison (arm A), each with 80% power and a 2-sided z test with alpha of 0.025. Assuming common SD at baseline and 6-month visit of 60 ng/ml,⁵¹ and a correlation of 0.90 between IGF-1 measures at baseline and 6-month⁴⁷, a total sample of 120 individuals (i.e. N=40 per arm) will allow the detection of a difference of 17.4 ng/ml (~10% reduction) or greater in change of IGF-1 over time between an active intervention arm and the control arm. With 20% random attrition, this trial will still be able to detect a difference

of 19.4 ng/ml or greater in change of IGF-1 over time between an active intervention arm and the control arm.

With the same sample size, the minimal detectable between arm difference in change of IGF1:IGFBP3 ratio over time were evaluated in a similar fashion for (1) arm B vs. A, and (2) arm C vs. A, each with 80% power and a 2-sided alpha of 0.025. Assuming common SD at baseline and 6-month visit of 11 using data available from the POWER trial,⁸¹ and a correlation of 0.80 between IGF-1:IGFBP3 ratio at baseline and 6-month⁴⁷, a total sample of 120 individuals (i.e. N=40 per arm) will allow the detection of a difference of 5.01 (~15% reduction) or greater in the change of IGF-1:IGFBP3 ratio over time between an active intervention arm and the control arm. With 20% random attrition, this trial will still be able to detect a difference of 5.67 or greater in change of IGF-1:IGFBP3 ratio over time between an active intervention arm and the control arm. We will explore the difference in outcome changes over time between arm B and C but this trial is not powered for this test, as the difference between these 2 arms may be small.

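### A cheap gain in precision: one shared baseline mean in the primary mixed model would cut variance by about 3-4% (IGF-1) and 7-8% (ratio) under the plan's own inputs

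*Combined protocol and SAP*

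**What the plan says.** Section 17.2 describes the mean model as "structured to include 2 binary intervention arm indicators (for Group B and C", with indicators for the 3-, 6- and 12-month visits and six group-by-time products. For the covariance, "the covariance model will employ a 4x4 unstructured covariance matrix to allow different outcome variances". Baseline is therefore part of the outcome vector, and the arm indicators give each arm its own baseline mean.

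The B versus A test is "evaluated through the regression coefficients of the Group B by 6month interaction term (B vs. A", and C versus A is handled in the same way. The secondary B versus C contrast at 6 months comes from this model too, as do "the 3 pairwise group comparisons of outcome changes at 12 months, which will be evaluated using the same model".

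On covariates: "Race and baseline BMI levels, the variables used for stratifying the randomization, will be included in the mean model". The section does not say whether they enter as main effects or by visit, and it does not name the baseline value of the outcome as a covariate.

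Section 7 places randomization after the coordinator confirms that the "individual meets all eligibility criteria, and all baseline data have been collected". Section 16 sets the planning inputs: "Assuming common SD at baseline and 6-month visit of 60 ng/ml" with a correlation of 0.90 for IGF-1, and "Assuming common SD at baseline and 6-month visit of 11 using data available from the POWER trial" with a correlation of 0.80 for the ratio. It assumes 40 per arm, 20% random attrition, and a two-sided alpha of 0.025 for each contrast.

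**The concern.** With a free baseline mean in every arm, the planned contrast subtracts the whole observed baseline difference between arms. Because allocation follows baseline collection, that difference is chance alone, and the two arm main effects estimate a quantity known to be zero. Subtracting all of it is not optimal when baseline and 6-month values correlate below 1 and have similar SDs. The best weight is the regression slope of the 6-month value on baseline, not 1.

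What is at stake is precision only. Section 16 says that resources fix the size at about 120, so precision is hard to buy with more participants. The samples that would supply the gain are already planned.

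**Working it through.** **1. The plan's own figures.** Detectable difference = (z(0.9875) + z(0.80)) × SD × √(2(1−r)) × √(2/n), with z-sum 3.083.
- IGF-1, n = 40: SE = 60 × √0.20 × √(2/40) = 6.000, giving 18.50 ng/ml (plan: 17.4). With n = 32: 20.68 (plan: 19.4).
- Ratio, n = 40: SE = 11 × √0.40 × √(2/40) = 1.556, giving 4.80 (plan: 5.01). With n = 32: 5.36 (plan: 5.67).

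The printed values do not reproduce. That is a separate matter: the percentage gains below depend on r, the SD ratio and attrition, not on the printed differences.

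**2. Complete data.** Let D0 and D6 be the observed arm differences at baseline and 6 months, and s = SD at 6 months / SD at baseline.
- Planned model: D6 − D0, variance proportional to 1 + s² − 2rs.
- Shared baseline mean: D6 − b·D0 with b = rs, variance proportional to s²(1−r²).
- At s = 1 the variance ratio is (1+r)/2 = 0.950 (IGF-1) and 0.900 (ratio).
- Estimating the slope from 120 participants in three arms multiplies this by about 1 + 1/115, giving 0.958 and 0.908. Detectable differences go from 18.50 to 18.11 ng/ml and from 4.80 to 4.57. Equivalent sample size: 40/0.958 = 41.7 and 40/0.908 = 44.1 per arm.

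**3. 20% attrition, large-sample formula** (40 per arm at baseline, 32 at 6 months, s = 1).
- Planned: 2·SD²·[(1−r²)/32 + (1−r)²/40].
- Shared: 2·SD²·(1−r²)/32.
- IGF-1: 7200 × (0.0059375 + 0.00025) = 44.55 against 42.75, a fall of 4.04%.
- Ratio: 242 × (0.01125 + 0.001) = 2.9645 against 2.7225, a fall of 8.16%.

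**4. 20% attrition, covariance estimated.** Maximum likelihood with an unstructured covariance was simulated for three arms of 40, with 200,000 trials per setting. Loss fell before or after the 3-month visit, and correlations were either equal or decaying with time. The 3-month SDs and correlations are assumptions.
- IGF-1: variance ratio 0.963-0.969. The detectable difference falls by 0.32-0.37 ng/ml. A contrast with 80% power under the planned model has 81.3-81.6%.
- Ratio: variance ratio 0.918-0.927. The detectable difference falls by 0.19-0.21. Power goes from 80% to 83.2-83.6%.

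**5. Unequal SDs.** Section 16 assumes s = 1; the unstructured covariance in Section 17.2 does not require it. Variance ratios, shared over planned, with 20% loss:

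| SD at 6 months / SD at baseline | IGF-1 | Ratio |
|---|---|---|
| 0.90 | 0.839-0.849 | 0.815-0.832 |
| 1.00 | 0.963-0.969 | 0.918-0.927 |
| 1.05 | 0.996-0.998 | 0.955-0.961 |
| 1.10 | 1.008 | 0.979-0.983 |
| 1/r (1.11; 1.25) | 1.008-1.009 | 1.009 |

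At s = 1/r the slope rs is 1, so the planned weight is already the best one. What remains is the cost of estimating the slope, about 0.9% of variance.

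**6. Race and BMI.** As time-constant main effects they cancel from the planned complete-data contrast. They do not cancel under a shared baseline mean. The shared-mean model was compared with a model of the follow-up values that has baseline outcome by visit as a covariate (complete data, r = 0.90, one covariate with an assumed coefficient of 0.5). With the covariate as a main effect, the two 6-month estimates differed from trial to trial by about 9% of the SE. They agreed to rounding only when the covariate entered by visit.

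**The case against.** The endpoint, the power calculation and the tested coefficient all concern change, so the planned model is coherent as it stands. It also already takes most of what baseline offers. Against a comparison of 6-month values alone (variance 1), change gives 2(1−r) = 0.20 and 0.40, while the best weighting gives 1−r² = 0.19 and 0.36. The plan therefore removes 80 of the 81 available points for IGF-1 and 60 of 64 for the ratio. The IGF-1 gain of 0.32-0.37 ng/ml is about a third of the gap between the printed 17.4 and the recomputed 18.50. Exact SD equality is a planning simplification, and no 6-month SD is reported. Section 17.2 also allows transformation, so the ng/ml figures may not carry over to the final scale.

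All of that stands as a limit on size. It does not remove the point: the contrast is still the arm difference in 6-month change, and the worst-case loss is far smaller than the gain under the plan's own inputs.

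A reader might go further than the documents allow, in three ways:
- **That the plan ignores baseline.** It does not; subtraction is a use of baseline, and step 2 shows that only the weight differs.
- **That the change is free.** A loss is possible, though it is under 1% of variance.
- **That adjusting follow-up values for baseline is the same analysis.** That holds only if race and BMI enter by visit, and Section 17.2 does not say that they do.

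**Conclusion.** The point holds as an optional, inexpensive improvement. Under Section 16's equal SDs, correlations and 20% attrition, one shared baseline mean lowers the variance of the primary contrasts by about 3-4% for IGF-1 and 7-8% for the ratio. This rests on the baseline draw preceding allocation, which Section 7 requires, and on the SD ratio. The gain is larger if the 6-month SD falls below baseline, nearly nil for IGF-1 at 1.05 times baseline, and at worst a loss of about 0.9% near 1/r times baseline. The attrition ranges also depend on assumed 3-month SDs, correlations and timing of loss.

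The 12-month contrasts come from the same model and would be affected too, but the documents give no correlation from which to size that gain. It would be wrong to infer that the planned analysis is biased or invalid; randomization protects it either way.

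**What to change.** In Section 17.2, remove the two arm main effects from the mean model and keep the three visit indicators and six group-by-time terms, so that all arms share one baseline mean. State that race and baseline BMI enter by visit. The group-by-6-month coefficients remain the tests.

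An acceptable alternative is to model the 3-, 6- and 12-month values with baseline outcome by visit as a covariate, again with race and BMI by visit. It captures essentially the same gain. Name one of the two as primary before arm-level data are seen, and keep the model as now written as a sensitivity analysis.

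The cost is SAP wording: no added participants, visits or assays, and the same estimand. There are two fewer arm parameters, offset by the extra race and BMI by visit terms. The statistical price is at most about 0.9% of variance in the worst case above.

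### As listed, race and baseline BMI have no visit interaction in the primary model, so with complete data they do not adjust the 6-month change contrast

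*Combined protocol and SAP*

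**What the plan says.** Section 7 states: "Randomization will be stratified by race and BMI". Section 17.2 defines the endpoint: "The primary endpoint of this trial is the 6-month change in level of IGF-1 and IGF1 to IGFBP-III ratio", for coach-directed against self-directed and metformin against self-directed.

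The same section builds the mean model from two arm indicators, three visit indicators and "the cross-product interaction terms between the group and time indicators (6 interaction terms"; for the errors, "the covariance model will employ a 4x4 unstructured covariance matrix". A separate sentence then says: "Race and baseline BMI levels, the variables used for stratifying the randomization, will be included in the mean model". Other variables that turn out imbalanced between arms may be added as needed.

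The primary contrasts are the two arm-by-6-month coefficients, "which will be evaluated through the regression coefficients of the Group B by 6month interaction term (B vs. A", and likewise for metformin.

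The only place where BMI is explicitly crossed with visit is a later exploratory analysis of effect modification, "including the 3-way interaction terms (Group indicator by Time indicator by BMI) in the primary analysis model". Subgroup-by-arm-by-visit terms, with race as one of the subgroups, are also exploratory.

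**The concern.** The plan puts the stratification factors into the primary model, and a reader will take the primary contrast to be adjusted for them. But the contrast is about change, and the listed terms let race and BMI affect only the overall level of IGF-1, equally at every visit. A factor that shifts baseline and 6 months by the same amount cannot explain any variation in change or correct an imbalance in it.

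After stratified randomization the arms are nearly balanced on the strata. If the strata predict change, the treatment contrast is really less variable than an unadjusted standard error says. The test then rejects too rarely under the null and loses power that the stratification has already made available. Section 16 fixes the size at about 120 by resources, so precision in the analysis is one of the few things left to improve.

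The same cancellation applies to any time-constant variable added because it looks imbalanced. Entered as a main effect, it would appear to correct the imbalance without doing so for change.

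**Working it through.** **Inputs.** From section 16: SD 60 ng/ml at baseline and 6 months, correlation 0.90, 40 per arm, two-sided alpha 0.025 per contrast, 80% power, 20% attrition. From section 17.2: the model terms above. Not in the documents and therefore assumed: the share R² of the variance of change explained by the strata.

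**Plan's own figure.** SD of change = 60·√(2·(1 − 0.90)) = 26.83. SE of the contrast = 26.83·√(2/40) = 6.00. Detectable difference = (2.2414 + 0.8416)·6.00 = 18.5 ng/ml. Section 16 states 17.4, where these inputs give 74.5% power. That mismatch is a separate matter. I use 18.5 below because it is the difference with 80% power on the plan's inputs.

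**Algebra.** Let μ(a,t) be the mean for arm a at visit t, and g·x the contribution of a time-constant covariate with one coefficient.

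- Mean at 6 months: μ(a,6) + g·x. Mean at baseline: μ(a,0) + g·x.
- Mean change: μ(a,6) − μ(a,0). The term g·x is gone.
- With arm by visit saturated, unstructured covariance and complete data, the likelihood splits into the changes from baseline (arm means only) and baseline given the changes (which contains g·x). The two parts share no parameters. The maximum-likelihood (ML) estimate is therefore the raw difference in mean change, and its SE does not involve x.

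**Numerical check, complete data.** The planned model was fitted by ML with and without race and BMI. In one simulated data set the two contrasts were 10.6190 and 5.3863, each with SE 5.8514, in both fits. Over 1,500 simulated trials with the plan's inputs the largest difference was 6e-13, and the mean SE was 5.906 either way.

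**Numerical check, about 20% missing.** The covariates now help to predict missing 6-month values. One simulation gave a root-mean-square shift of 0.25 ng/ml (0.25/5.906, about 4% of the complete-data SE). Another, over several dropout patterns, gave mean absolute shifts of 0.2 to 0.6 ng/ml, a maximum of 2.7, and a change in mean SE of at most about 0.03.

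**Consequence if the strata predict change.** Assume stratification balances the strata well, so the true SD of the contrast is 6.00·√(1 − R²) while the planned analysis still reports 6.00.

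- True error of the planned test = 2·Φ(−2.2414/√(1 − R²)).
- Power as planned = Φ((18.5 − 2.2414·6.00)/(6.00·√(1 − R²))).
- Power with visit interactions = Φ(18.5/(6.00·√(1 − R²)) − 2.2414).

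For R² = 10%: true SD = 6.00·0.9487 = 5.69. Error: 2.2414/0.9487 = 2.363, giving 0.018. Power as planned: (18.5 − 13.45)/5.69 = 0.887, giving 81.3%. With interactions: 18.5/5.69 − 2.2414 = 1.009, giving 84.3%.

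| Assumed R² | True error (nominal 0.025) | Power as planned | Power with visit interactions | Gain, points |
|---|---|---|---|---|
| 0% | 0.025 | 80.0% | 80.0% | 0 |
| 5% | 0.021 | 80.6% | 82.2% | 1.6 |
| 10% | 0.018 | 81.3% | 84.3% | 3.0 |
| 15% | 0.015 | 81.9% | 86.5% | 4.6 |

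**Behaviour of the fix.** With visit interactions, complete data and an assumed R² of 10%, the simulated mean ML SE was 5.55 against a true SD of 5.65. Using 5.55 with the nominal critical value gives 2.2414·5.55/5.65 = 2.202, an error of about 0.028. ML is therefore slightly too optimistic at this sample size.

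**The case against.** Four points can fairly be made for the plan.

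1. It never says main effects only. The covariates come in their own sentence, which gives no functional form. This stands as a caution: the absence of visit interactions is the natural reading, not stated text. The reading is strong, because section 17.2 counts its interaction terms, all six are arm by visit, and BMI is crossed with visit explicitly only in an exploratory analysis. If the authors did intend such terms, the same sentence is needed.

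2. A reader might infer that the adjustment does nothing at all. That is exact only with complete data. Section 16 allows 20% attrition and section 17 relies on a likelihood analysis under missing at random, where race and BMI do contribute a little. They also adjust comparisons of level.

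3. A reader might infer a material loss of power. The documents do not support that. Section 3.4 links BMI to the level of IGF-1 cross-sectionally, but nothing says how far race or BMI predicts change. The range has to include zero, where there is neither loss nor gain.

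4. A reader might infer that the primary result is biased or its error rate inflated. With complete data it is neither; any departure is conservative. A bias of about −2.2 ng/ml (about 0.1 with visit interactions) appeared only in a constructed case in which dropout depended on race in opposite directions between arms and race and BMI strongly predicted change. Nothing in the documents suggests this pattern.

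The exploratory interaction terms do not answer the point, since they do not enter the primary test.

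**Conclusion.** The point holds in a limited form. On the natural reading of section 17.2, race and baseline BMI cancel exactly from the primary contrast when data are complete, and they matter only slightly with about 20% missing. The same holds for any other time-constant variable added for imbalance. The algebra is certain given that reading, and it applies equally to the IGF-1:IGFBP-3 ratio and to the 12-month contrasts.

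The consequence is conditional. If the strata explain 5 to 15% of the variance of change, the true error of the 0.025 test is 0.021 to 0.015, and 1.6 to 4.6 points of power at 18.5 ng/ml are forgone. At 0% nothing is lost. These figures rest on an assumed R², normal theory, complete data and good balance from the stratified blocks. This is a cheap improvement to precision and clarity; the planned test is not invalid.

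**What to change.** Replace the covariate sentence in section 17.2 with: *Race and BMI stratum, as used for randomization, and any other time-constant adjustment variable, enter the mean model together with their interactions with visit. The primary contrasts remain the arm-by-6-month coefficients.*

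If the authors prefer to keep main effects only, the plan should say so, and say that the change contrast is then not adjusted for these variables when data are complete.

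The cost is one sentence and a few extra mean parameters: six if both strata are binary (two covariates times three follow-up visits). That is an assumption, since the documents give neither the race categories nor the BMI cut-points. Because the ML standard error was slightly too small in simulation, a small-sample method such as REML with Kenward-Roger degrees of freedom is advisable. That combination was not itself simulated here.
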